Intended Use:	The Trima Accel system is an automated blood cell separator intended for use in collecting blood components for later transfusion into patients.
Study Centers Planned:	At least 2 and up to 8 Blood Centers in the United States
Objective:	To verify that platelets collected on the Trima Accel system with Version 7.0 software enhancements and stored in PAS meet the FDA requirements for leukoreduction ($< 5.0 \times 10^6$ residual white blood cells [WBC] per transfusable unit).
Rationale:	The study is designed to evaluate changes to the Trima Accel software to ensure the modified software meets the FDA acceptance criteria for leukoreduction and platelet yield. The operating range for the system flow rates, anticoagulant ratios, storage conditions, and centrifugal forces are the same as the currently cleared Trima Accel system. There are no changes to the environment or storage conditions for platelets; therefore, no in vitro or in vivo platelet quality data will be collected.
Outcome Measures:	
Primary Endpoint: The proportion of platelet units with an acceptable residual WBC level. Acceptable residual WBC counts are: singles = residual WBC level $< 5.0 \times 10^6$; doubles = residual WBC level $< 8.0 \times 10^6$ or $< 5.0 \times 10^6$ for each transfusable unit; and triples = residual WBC level $< 12.0 \times 10^6$ or $< 5.0 \times 10^6$ for each transfusable unit.
 
Secondary Endpoint: The proportion of platelet units with an acceptable platelet yield. Acceptable platelet yield for single, double and triple platelet products are: platelet yield $\geq 3.0 \times 10^{11}$ for singles, platelet yield $\geq 6.2 \times 10^{11}$ for doubles, and platelet yield $\geq 9.3 \times 10^{11}$ for triples.

Safety Measures:	Safety will be monitored through collection of adverse events (AEs), serious adverse events (SAEs), and unanticipated adverse device effects (UADEs).
Inclusion Criteria:	
 1. Age 18 years or older. 2. Meets the inclusion criteria defined by the Blood Center for an apheresis platelet with PAS collection on the Trima Accel system. These criteria are based on FDA guidance and American Association of Blood Banks (AABB) standards. Note: subjects who are deferred from volunteer community donations because of travel restrictions, piercings, or tattoos may participate in the study, as products are not transfused. 3. Has given written informed consent.

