10.2.2 Apheresis Procedure

Plateletpheresis will be per site standard practice and per applicable FDA guidelines such as the “Guidance for Industry and FDA Review Staff: Collection of Platelets by Automated Methods, December 2007” and the “Guidance for Industry: Pre-Storage Leukocyte Reduction of Whole Blood and Blood Components Intended for Transfusion, September 2012”.^{9,10}

Apheresis procedures will be run according to the instructions and precautions described in the Version 6.0 Trima Accel Operator’s Manual and the Version 7.0 user change summary.

The following procedures will be performed:

1. Venipuncture.
2. Collect venous whole blood sample.
 - a. Complete blood count (hemoglobin or hematocrit and platelet count).
3. Update Trima Accel device with updated platelet count and hemoglobin or hematocrit.

4. Perform apheresis procedure.
5. Record the following:
 - a. Type of cuff used.
 - b. Trima procedure details.
 - c. AEs, SAEs and UADEs.
 - d. Medical interventions to treat AEs, if applicable.
 - e. Device deficiencies.

This will conclude the subject's participation.

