15.2.2 Secondary Endpoint

The secondary endpoint of platelet yield will be summarized for single, double, and triple platelet products. Separately for single, double, and triple platelet products, the lower one-sided 95% exact binomial confidence intervals will be calculated for the proportion of platelet units with an acceptable platelet yield. If 16 or fewer failures are observed, then the confidence interval will suggest that the true success rate is at least 75% with 95% confidence for the given platelet product.

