### 3.2 Study Populations

Analysis populations for this clinical investigation will be the Full Analysis Set (FAS) and Safety Populations.

For all analyses by platelet product, the platelet product type (single, double, triple, or unassigned) will be determined from the calculated platelet yield (see Section 3.3) using the following.

- If the platelet yield, rounded to the nearest tenth, is  $\geq 9.3 \times 10^{11}$ , then the product will be analyzed as a triple.
- Otherwise, if the platelet yield, rounded to the nearest tenth, is  $\geq 6.2 \times 10^{11}$ , then the product will be analyzed as a double.
- Otherwise, if the platelet yield, rounded to the nearest tenth, is  $< 6.2 \times 10^{11}$ , then the product will be analyzed as a single.
- Otherwise, if the procedure was not started, not completed or the platelet yield could not be determined for some other reason, as per the protocol analysis exclusion criteria, then the subject will be analyzed as “Unassigned”.

The Safety Population will include all subjects enrolled in this trial for whom at least 1 apheresis procedure is initiated. A procedure will be considered to have been initiated if a Trima procedure start date and time are present. The Safety Population will be used for all summaries except the primary and secondary endpoints and the derived apheresis related parameters.

Due to the design of the study, a given subject may be enrolled in the study on multiple occasions. These subjects may also qualify for the Safety Population more than once. If this occurs, the subjects will be analyzed separately for each enrollment.

The Full Analysis Set (FAS) will be defined separately for single, double, and triple platelet products and will not include any repeat subjects. The FAS for a given platelet product will consist of all collections that do not meet any of the exclusion criteria specified below. The FAS will be used to examine the primary and secondary endpoints and the derived apheresis related parameters.

Data points will be excluded from the FAS analysis in the following situations:

1. Inability to collect a complete unit due to:
  - a. Subject issues (inadequate access, reaction, needle abort, procedure disqualification upon Trima Accel device update of subject platelet count and hemoglobin or hematocrit).
  - b. Decision to stop procedure by subject, Investigator, nursing staff or operator.

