### 3.5 Secondary Endpoints

- Proportion of platelet units with an acceptable platelet yield for single platelet products.
- Proportion of platelet units with an acceptable platelet yield for double platelet products.
- Proportion of platelet units with an acceptable platelet yield for triple platelet products.

Acceptable platelet yield is defined as following, where the platelet yield is calculated from the formula in Section 3.3:

For single platelet products: platelet yield, rounded to the nearest tenth,  $\geq 3.0 \times 10^{11}$ .

For double platelet products: platelet yield, rounded to the nearest tenth,  $\geq 6.2 \times 10^{11}$ .

For triple platelet products: platelet yield, rounded to the nearest tenth,  $\geq 9.3 \times 10^{11}$ .

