**Secondary Endpoint Acceptance Criteria**

Parameter	Measured	Acceptance Criteriaa
Platelet yield – Single Unit	Platelet concentration × volume	Platelet yield is $\geq 3.0 \times 10^{11}$
Platelet yield – Double Unit	Platelet concentration × volume	Platelet yield is $\geq 6.2 \times 10^{11}$
Platelet yield – Triple Unit	Platelet concentration × volume	Platelet yield is $\geq 9.3 \times 10^{11}$

a These yields represent typical lab minimums for splitting into double and triple platelet products.

Platelet yield will be summarized separately for single, double, and triple platelet products. The summaries will include N, mean, standard deviation, median, minimum, and maximum.

Separately for single, double, and triple platelet products, the lower one-sided 95% exact binomial confidence intervals (Clopper-Pearson) will be calculated for the proportion of platelet units with an acceptable platelet yield. If the lower one-sided confidence interval is greater than 75%, then it will be concluded that the proportion of platelet units with an acceptable platelet yield is at least 75% for the given platelet product.

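### SAP 3.2 assigns product type with the same yield cut-offs that SAP 3.5 uses to score yield, so no analysed double or triple can fail the secondary endpoint

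*SAP*

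**What the plan says.** SAP 3.2 sets one typing rule for every analysis by product: "the platelet product type (single, double, triple, or unassigned) will be determined from the calculated platelet yield", using the SAP 3.3 formula rounded to the nearest tenth. At 9.3 × 10¹¹ or more, "then the product will be analyzed as a triple". Failing that, at 6.2 × 10¹¹ or more, "then the product will be analyzed as a double". Any lower yield is a single, with no lower bound. The unassigned class takes only procedures that were not started, were not completed, or have no determinable yield.

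SAP 3.5 scores acceptable yield from the same formula. "For triple platelet products: platelet yield, rounded to the nearest tenth", must be at least 9.3 × 10¹¹. The limit is 6.2 × 10¹¹ for doubles and 3.0 × 10¹¹ for singles.

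Protocol 15.1 and SAP 3.1 allow 16 yield failures among 93 products of each type. Protocol 15.2.2 puts it this way: "If 16 or fewer failures are observed, then the confidence interval will suggest that the true success rate is at least 75" per cent, with 95% confidence. SAP 3.7.3 applies the same test through the one-sided 95% Clopper-Pearson lower limit.

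The protocol has no yield-based typing rule. Protocol 10.3 (reason 3) and 15.4 (item 2) describe type as what the donor qualifies for on platelet count, which is known before any yield exists.

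**The concern.** Reaching the cut-off is both the condition for entering the double or triple group and the definition of success within it. A collection that misses its minimum leaves the group before it can be counted as a failure.

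Yield is not incidental. The rationale in the Protocol Synopsis is "to ensure the modified software meets the FDA acceptance criteria for leukoreduction and platelet yield", and SAP 3.7.3 plans a formal conclusion that at least 75% of each type is acceptable. For doubles and triples that conclusion would carry no evidence.

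The descriptive tables do not fill the gap. Under SAP 3.7.3, "Platelet yield will be summarized separately for single, double, and triple platelet products", and these summaries and those of SAP 3.7.4 use the same typing. After rounding, the reported minimum cannot fall below 9.25 × 10¹¹ for triples or 6.15 × 10¹¹ for doubles.

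**Working it through.** **1. The plan's own figure.** Inputs: n = 93, one-sided alpha 0.05 and a 75% threshold (Protocol 15.1, SAP 3.1 and 3.7.3). The Clopper-Pearson lower limit for x successes in n is the 5th percentile of Beta(x, n − x + 1).

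- 16 failures: 77/93 gives 0.7505, above 0.75.
- 17 failures: 76/93 gives 0.7385, below 0.75.

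The 16-of-93 rule is correct, with an exact one-sided error of 0.0489. If failures can occur, it is a real test:

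| True rate of acceptable yield | Chance of 16 or fewer failures in 93 |
|---|---|
| 70% | 0.4% |
| 75% | 4.9% |
| 80% | 30.0% |
| 85% | 77.5% |
| 90% | 99.0% |

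**2. The two SAP rules side by side** (rounded yield, × 10¹¹).

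| Class | Entry rule, SAP 3.2 | Success rule, SAP 3.5 | Can it fail? |
|---|---|---|---|
| Triple | ≥ 9.3 | ≥ 9.3 | No |
| Double | ≥ 6.2 and < 9.3 | ≥ 6.2 | No |
| Single | < 6.2 | ≥ 3.0 | Yes, below 3.0 |

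Both rules were applied to a grid of yields from 0.1 to 15.0 in steps of 0.001. All 3,101 values classed as double and all 5,749 classed as triple met their criterion.

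**3. Consequence for the doubles and triples tests.** With no failures the lower limit is 0.05^(1/n): 0.741 at n = 10, 0.762 at n = 11 and 0.968 at n = 93. The 75% test passes as soon as the class holds 11 products.

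**4. Consequence for singles.** The documents give no expected yield success rate, so this step is illustrative. Assume 93 collections per targeted type, a common true success rate p, failing doubles that still reach 3.0, failing triples that drop only to double, and no targeted single reaching 6.2.

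- Singles group size: 93 + 93(1 − p) = 93(2 − p).
- Successes: 93p + 93(1 − p) = 93.
- Apparent rate: 1/(2 − p).

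| True p | Apparent singles rate |
|---|---|
| 0.50 | 0.667 |
| 0.60 | 0.714 |
| 0.75 | 0.800 |
| 0.90 | 0.909 |
| 0.95 | 0.952 |

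**5. Illustrative simulation.** Assumptions: 93 per targeted type, all completed collections analysed, normal or log-normal yields, CV 5% to 20%, and means set so that the rounded yield meets the minimum with probability p. There were 20,000 runs per setting.

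| | By targeted type | By SAP 3.2 |
|---|---|---|
| p = 0.75, doubles and triples pass | about 5% | 100% |
| p = 0.75, singles pass | about 5% | about 30–32% |
| p = 0.50, doubles and triples pass | 0% | 100% |

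At p = 0.75 the mean single/double/triple group sizes become about 116/93/70 (CV 5–12%) or 118/85/76 (CV 20%, normal yields).

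**6. A conditional side effect on the primary endpoint.** If recruitment counts targeted types, an analysed group may fall below 93. The WBC rule has no slack there: 92/93 gives 0.95001, but 91/92 gives 0.9495. A group of 59 to 92 passes only with no failures (59/59 gives 0.9505, 58/58 gives 0.9497). Protocol 10.3 and 15.4 refer to donations completed or products collected, without saying whether they are counted by targeted or achieved type.

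**The case against.** The best case for the SAP is that the cut-offs are how products are labelled in practice. Protocol Table 7-2 calls them typical laboratory minimums for splitting a collection. A collection of 8.5 × 10¹¹ is then a double, whatever was intended. For the WBC endpoint this stands, because the limit that matters is the one for the product actually made. For the yield endpoint it does not, because a label assigned by yield cannot also test yield.

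It can also be said that the stated objective is leukoreduction, that yield is secondary, and that the primary result is not undone. That is true, and it bounds the damage. But the protocol's rationale names yield and the SAP draws a formal conclusion on it.

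SAP 1.0 and 3.7 promise listings of all eCRF data. If the targeted product is recorded, a reader could trace shortfalls there. A listing does not repair the test or the summary tables.

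The exclusions do not help either. A completed run with a low yield meets none of them by that fact alone, and an excluded run would still not count as a failure.

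The singles inflation depends on assumptions and is small when performance is good: at p = 0.90 it is under one percentage point (0.909 − 0.900), and a test by targeted type would already pass 99.0% of the time. The simulation's CVs and distributions are assumed, and it does not model the exclusions. The finding for doubles and triples needs neither.

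**Conclusion.** The concern holds and the SAP should be changed before analysis. For doubles and triples, the yield success rate is 100% and the 75% test passes with 11 or more products, at any true rate. This follows from SAP 3.2 and 3.5 alone and needs no assumption about yields.

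The effect on singles is secondary and conditional: about 5 points at a true 75% under the assumptions in step 4, and negligible above 90%. The loss of slack in the WBC test arises only if recruitment is counted by targeted type, which the documents leave open.

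**What to change.** - **Typing for yield.** In SAP 3.2, for the secondary endpoint and its summaries, define type as the product the Trima was set to collect after the day-of platelet-count update. Count a rounded yield below that type's minimum as a failure.
- **Cross-table.** Tabulate targeted against achieved type, so that re-labelled collections are visible.
- **Typing for WBC.** Keep achieved type for the primary endpoint, and also report WBC success by targeted type.
- **The count of 93.** State which type counts towards 93. Protocol 15.3 and SAP 3.2 define one full analysis set per product for both endpoints. With two typings, only one endpoint can be sure of its designed number. The SAP should say which, and should judge the other by its confidence limit at the actual n.
- **Data check.** Before analysis, confirm that the "Trima procedure details" recorded under Protocol 10.2.2 include the targeted product.

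The cost is SAP wording, one derivation and one table, with no change to how collections are run. If the eCRF lacks the targeted product, it must be retrieved from the procedure records. The reported double and triple yield rates may then fall below the 100% that the present rule guarantees.

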**3.7.5 Safety Analysis**

All adverse events will be coded using MedDRA and reported by SOC and preferred term. The focus of the adverse event summaries will be on treatment-emergent adverse events. Adverse events will be considered treatment-emergent if they occur on or after the start of the apheresis procedure, as defined in Section 3.2. Adverse events (AEs), serious adverse events (SAEs), and unanticipated adverse device effects (UADEs) will be summarized with frequencies and percentages. Additional summaries of AEs will be presented for the maximum reported severity and relationship to device and procedure. AEs leading to study or procedure discontinuation will also be tabulated. Summaries will be presented by platelet products (single, double, triple, and unassigned) and overall.

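### SAP 3.2 applies the yield cut-offs before the non-completion rule, so a stopped procedure with a measured yield is placed in a product column instead of Unassigned (minor; Safety Population tables only)

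*SAP*

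**What the plan says.** SAP 3.2 states that, for all analyses by platelet product, the type "will be determined from the calculated platelet yield". The rules form a chain, with yield in units of 10^11 rounded to the nearest tenth:

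1. Yield of at least 9.3: "then the product will be analyzed as a triple".
2. Otherwise, yield of at least 6.2: "then the product will be analyzed as a double".
3. Otherwise, yield below 6.2: "then the product will be analyzed as a single". There is no lower limit.
4. "Otherwise, if the procedure was not started, not completed or the platelet yield could not be determined for some other reason", by reference to the protocol's analysis exclusions: Unassigned.

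The Safety Population in the same section takes in "all subjects enrolled in this trial for whom at least 1 apheresis procedure is initiated", so stopped procedures are part of it. It serves every summary except the primary and secondary endpoints and the derived apheresis parameters. Demographics (SAP 3.7.1) and disposition with reasons for discontinuation (SAP 3.7.2) are split by product type. For adverse events, SAP 3.7.5 says: "Summaries will be presented by platelet products (single, double, triple, and unassigned) and overall".

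**The concern.** The fourth rule names non-completed procedures as Unassigned, but its position in the chain disables that condition whenever a yield value exists. A programmer who codes the list as written would put a stopped procedure into a product column according to how much had been collected when it stopped. For example, an intended triple stopped with 4.0 ×10^11 in the bag would be tabulated as a single.

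The tables concerned are the ones in which stopped procedures carry most information: reasons for discontinuation, adverse events, and adverse events leading to discontinuation. Protocol 13.2 provides for stopping when moderate or severe adverse events occur, so stopped procedures can be expected to include a higher share of events than completed ones. At stake is whether a reader of the by-product safety tables can take each column to describe completed products of that type.

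**Working it through.** **1. The plan's own figures.** These are the failure limits for 93 products per type (SAP 3.1), using the one-sided 95% Clopper-Pearson lower bound (SAP 3.7.3). With n products and s successes, the bound is the 5% quantile of Beta(s, n − s + 1).

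- Residual WBC, n = 93, 1 failure, Beta(92, 2): 95.0006%. With 2 failures it is 93.38%. With n = 92 and 1 failure it is 94.95%, so 93 is the minimum for 1 failure.
- Yield, n = 93, 16 failures, Beta(77, 17): 75.05%. With 17 failures it is 73.85%.

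Both stated limits reproduce. They do not depend on the rule order, because they apply to the full analysis set (FAS; see step 4).

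**2. The classification rules applied to a procedure that was not completed.**

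| Yield (×10^11) | Order as written | Completion tested first |
|---|---|---|
| none | Unassigned | Unassigned |
| 0.4 | single | Unassigned |
| 2.9 | single | Unassigned |
| 3.0 | single | Unassigned |
| 6.14 (rounds to 6.1) | single | Unassigned |
| 6.2 | double | Unassigned |
| 7.5 | double | Unassigned |
| 9.3 | triple | Unassigned |
| 9.6 | triple | Unassigned |

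As written, only a missing yield reaches Unassigned. A stopped procedure becomes a single below 6.2, a double from 6.2 to 9.2 and a triple from 9.3. Single is likely to receive most of them: a stopped double that has not reached 6.2 goes there, as does a triple stopped before 6.2.

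**3. Can a stopped procedure have a yield?** The formula in SAP 3.3 needs a bag weight, two platelet counts and a dilution factor. Protocol 10.2.3 lists the corresponding data for collected products and does not limit them to completed procedures. The exclusions in SAP 3.2 list unavailable assay results (4g) separately from incomplete collection through equipment, subject or centrifuge problems (4a to 4c), which is consistent with incomplete collections that do have results. Nothing requires the measurement for a stopped procedure, and nothing excludes it.

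**4. Which outputs are touched?** The FAS drops incomplete collections through exclusions 1, 2 and 4 in SAP 3.2, and Protocol 8.1 makes completion part of the definition of evaluable. The primary and secondary endpoints and the derived parameters all use the FAS. What remains is the set of Safety Population tables by product. Their overall column is the same under either order.

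**5. Size.** The documents do not report how many stopped procedures had a measured yield. The illustration below rests entirely on assumptions: 93 completed singles with a 10% adverse event rate, and k stopped procedures, all with yield below 6.2 and a 50% rate. The single-column rate is then (9.3 + 0.5k)/(93 + k):

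- k = 0: 9.3/93 = 10%
- k = 5: 11.8/98 = 12.0%
- k = 20: 19.3/113 = 17.1%
- k = 30: 24.3/123 = 19.8%

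This shows the direction and how the result depends on k. It is not an estimate for this trial.

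**The case against.** The best defence is the wording of the fourth rule. By adding undetermined yield for some other reason after non-completion, it treats non-completion as itself a reason for having no yield. If stopped products are never weighed and counted, every stopped procedure has a missing yield, reaches the fourth rule and becomes Unassigned, and the order does no harm. This reading is plausible and probably reflects what the authors assumed. It makes the problem conditional but does not remove it, because neither document says that yield is left uncalculated for a stopped procedure.

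It can also be said that the tables are descriptive, that all eCRF data are listed (SAP 3.7), and that adverse events leading to discontinuation are tabulated in their own right. That stands, and it is why the point is minor.

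Three stronger readings are tempting, and the documents do not support them:

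- **All stopped procedures with a measured yield become singles.** Those at 6.2 to 9.2 become doubles, and those at 9.3 or above become triples.
- **A triple stopped at 4.0 ×10^11 could enter the FAS for singles, because that yield exceeds the single limit of 3.0.** Exclusion 1b names a decision to stop, exclusion 4 covers incomplete collection, and Protocol 8.1 requires a completed product. Protocol 9.4 treats failure to complete the anticipated procedure as discontinuation and allows rescreening after it. The term complete unit is not defined, but the natural reading keeps such procedures out.
- **The safety comparison between products is wrong by construction.** No such comparison is planned. SAP 3.7.5 provides frequencies and percentages, and any misplacement depends on stopped products being measured.

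**Conclusion.** The point holds as a minor drafting defect. The list in SAP 3.2, taken literally, gives a classification that its own fourth rule contradicts: a stopped procedure with a measured yield is filed under single, double or triple by its partial yield instead of Unassigned.

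The consequence rests on one assumption that the documents leave open, namely that at least some stopped products are weighed and counted. If so, the demographic, disposition and adverse event tables by product, including adverse events leading to discontinuation, attribute those procedures and their events to a column that the fourth rule did not intend, probably most often single. If not, nothing changes.

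The number affected is unknown. The rationale for protocol Version 4.0 says that screen failures and excluded procedures exceeded expectation, but gives no count of stopped procedures with a measured yield. No conclusion on leukoreduction or platelet yield is at risk.

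**What to change.** Either of two edits to SAP 3.2 is enough:

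- move the Unassigned rule (not started, not completed, or yield not determinable) to the top of the list and apply the three yield cut-offs only to completed procedures; or
- keep the order and state that platelet yield is not calculated for incomplete procedures.

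Either is a change to one list, needs no new data and leaves the sample size and endpoint analyses as they are. Its limit should be understood: stopped procedures move out of the product columns into Unassigned, but are not returned to the product that was intended. The double and triple columns would therefore still not include stopped doubles and triples, and stopped singles would leave the single column.

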#### 3.7.1 Demographic and Baseline Characteristics

Demographic and baseline characteristics will be summarized by platelet products (single, double, triple, and unassigned) and overall. Categorical variables (such as gender and race) will be summarized by frequency and percentage. Continuous variables (such as weight and height) will be summarized by N (number of non-missing observations), mean, standard deviation, median, minimum, and maximum.

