#### 3.7.2 Disposition

Study completion status and reasons for discontinuation will be displayed by platelet products (single, double, triple, and unassigned) and overall using frequencies and percentages.

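### Does it matter that SAP 3.2 classes never-started procedures as Unassigned but builds the tables showing that column only from donors with a Trima start?

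*SAP*

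**What the plan says.** The product-type rule in SAP 3.2 ends with a catch-all. A subject is analysed as Unassigned "if the procedure was not started, not completed or the platelet yield could not be determined for some other reason", and the clause closes by pointing to the protocol's analysis exclusions. The section then restricts the Safety Population to enrolled subjects with an initiated procedure, and adds: "A procedure will be considered to have been initiated if a Trima procedure start date and time are present". The scope of that population follows: "The Safety Population will be used for all summaries except the primary and secondary endpoints and the derived apheresis related parameters". The only other population, the Full Analysis Set (FAS), is made up of collections and serves the endpoints and derived parameters. No all-enrolled set is defined.

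Three SAP sections carry an Unassigned column, and none names a population of its own:

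- 3.7.1: "Demographic and baseline characteristics will be summarized by platelet products (single, double, triple, and unassigned) and overall".
- 3.7.2: "Study completion status and reasons for discontinuation will be displayed by platelet products (single, double, triple, and unassigned) and overall".
- 3.7.5: "Summaries will be presented by platelet products (single, double, triple, and unassigned) and overall".

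On adverse events, SAP 3.7.5 states: "The focus of the adverse event summaries will be on treatment-emergent adverse events". It defines that term as follows: "Adverse events will be considered treatment-emergent if they occur on or after the start of the apheresis procedure, as defined in Section 3.2". Protocol 15.2.3 plans tables of every event reported in the safety population, and protocol 13.4 records events from consent onward. SAP 3.7 lists everything on the eCRFs.

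**The concern.** One sentence of SAP 3.2 gives never-started procedures a column, and another keeps them out of every table that has it. Protocol 9.4 counts a donor as enrolled from consent, so the disposition table would not reconcile with the number enrolled. That number is of interest here, because Version 4.0 of the protocol raised the enrolment cap after screen failures and analysis exclusions ran above expectation. A reader who wanted to know how many donors fell out before a start would have to count them from listings.

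The second worry is adverse events. Screening under protocol 10.1 may include a venipuncture up to 30 days before the procedure. An event at that visit precedes the start, so in a donor who later starts it belongs in the table of protocol 15.2.3 but not in a treatment-emergent one. If only treatment-emergent tables were made, the report would fall short of the protocol.

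**Working it through.** **1. Who is lost.** The three routes to Unassigned in SAP 3.2, set against the start-stamp rule:

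| Route to Unassigned | Start stamp | In the 3.7.1, 3.7.2 and 3.7.5 tables |
|---|---|---|
| Started but not completed | yes | yes |
| Yield not determinable after a start | yes | yes |
| Never started | no | no, listings only |

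The never-started count is 0 by construction in 3 of 3 sections. The column itself is not empty, since two of the three routes feed it. A classification rule that reaches further than one population is loose drafting, but it does not make the tables impossible to produce. If the closing reference to the analysis exclusions governs the whole clause, screen failures were never meant to be Unassigned. The affected donors would then be those excluded under protocol 15.4, such as platelet-count stops. Item 2 of that section speaks of stopping a procedure, so these donors may well have a stamp.

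**2. How many.** Neither document says. The cap rose by 450 − 350 = 100, and 100/350 = 28.6%, but that increase covers screen failures and analysis exclusions together. Suppose, as an assumption, that enrolment reaches the cap and exactly the 279 target procedures (3 × 93) are evaluable. Then 450 − 279 = 171 enrolments (171/450 = 38%) are not evaluable. The never-started are an unknown part of these, so the range is 0 to 171. This bounds the number without estimating it.

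**3. Endpoints.** The one-sided 95% Clopper-Pearson lower limit for x successes in n is the 5% quantile of Beta(x, n − x + 1).

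- Residual WBC, 1 failure: x = 92, n = 93, Beta(92, 2), limit 0.95001. With 2 failures it is 0.93385. The plan's rule of at most 1 failure in 93 is reproduced.
- Platelet yield, 16 failures: x = 77, n = 93, Beta(77, 17), limit 0.75050. With 17 failures it is 0.73852. The plan's rule of at most 16 failures is reproduced.

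A donor with no collection enters neither x nor n, so these results are the same whatever population the descriptive tables use.

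**4. Disposition.** Protocol 9.4 separates a screen failure (not eligible) from a procedure discontinuation (not completed after venipuncture). SAP 3.7.2 plans completion status and discontinuation reasons. Leaving screen failures out of that table fits the protocol's distinction, and neither document promises a full enrolment flow.

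**5. Adverse events.** There are two groups.

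- *Donors who never start.* Protocol 15.2.3 confines its tables to the safety population, and protocol 15.3 requires an initiated procedure, as the SAP does. The two documents agree.
- *Donors who start later.* SAP 3.7.5 opens by committing to code and report every adverse event by MedDRA class and term. It then summarises adverse events, serious events and unanticipated device effects with no treatment-emergent limit in that sentence. A focus on one subset does not exclude the rest, so the protocol's table can be produced under this text.

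In both groups the events are listed (SAP 3.7), and serious events from consent onward go to the sponsor within 24 hours (protocol 13.7.2).

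**The case for a change.** The strongest case for a change is that the two sentences of SAP 3.2 cannot both be followed for a never-started donor, that no text overrides the blanket rule, and that putting it right would cost a line of wording and no new data. Listings do not replace a table that already has a column for these donors. Some of them may also be discontinuations in the protocol's own sense. Protocol 10.3 item 3 covers a donor whose venous platelet count places them in a product group that is already full. Protocol 9.4 counts non-completion from venipuncture, while the SAP counts from the start stamp, and neither document says how the two are timed. If the stamp comes later, such a donor drops out of the table meant to show reasons for stopping. A rescreened donor gets a new number and each enrolment is analysed separately, so a later success does not bring the earlier attempt back.

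All of this stands as a description of the wording. It does not show that a conclusion would be wrong. Reasons for discontinuation are on the eCRF under protocol 10.3, so the count can be recovered. The presence of never-started procedures in the Unassigned definition also tells a programmer that someone wanted them shown.

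**Conclusion.** The literal reading is right, but the plan need not change. It is a gap in the stated population of a descriptive table, of a kind that analysts close sensibly when they build the disposition display. The effect on the primary and secondary results is exactly zero. No stated sample size, precision or decision rule moves. The effect on adverse event tables is unknown and may be nil, because the protocol sets the same population and SAP 3.7.5 permits a table of all events. The cost of leaving the text alone is that a reader might have to take the never-started count from listings.

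This rests on two assumptions. The first is that the listings are complete, as SAP 3.7 says. The second is that the opening sentence of SAP 3.7.5 is carried out as written, so that events before the start in treated donors are reported and not filtered out.
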